3. SYNOPSIS

Title of Study:	Safety and Performance of PEEK Anchors (DYNOMITE°, SPYROMITE°, RAPTORMITE°, FOOTPRINT° ULTRA PK SL) in Extremities		
Study Design:	Multi-center, retrospective case series		
Study Type:	Post-market, clinical follow-up		
Study Product:	PEEK Extremity Suture Anchors RAPTORMITE° 3.0 PK W/NDL, 2 0 ULTRABRA DYNOMITE° 2.0 PK W/NDL, 1 2-0 ULTRABRAID SPYROMITE° 2.0 PK W/1 2-0 ULTRABRAID WH FOOTPRINT ULTRA PK 4.5 mm, SL FOOTPRINT ULTRA PK 5.5 mm, SL		
Study Purpose:	Assess safety and performance post-market of the PEEK suture anchor devices to address clinical data gaps for Medical Device Regulations (MDR).		
Primary Objective:	Safety and performance of the study devices in extremities over a time period of 6 months after intervention.		
Secondary Objective:	Safety and performance of the study devices in extremities over a time period of 12 months after intervention.		
Statistical Rationale:	The sample size for this study is determined based on the feasibility of recruitment, enrollment and follow-up considerations. The study is therefore not powered for any statistical hypothesis testing but will be able to estimate a clinical success rate of 91% with a 95% confidence interval (CI) of 80% to 100%.		
Sample Size:	Minimum, n= 80		
	Maximum, n= 480		
	Enrollment distribution:		
		PEEK Anchor	Minimum
	RAPTORMITE°	20	120
	DYNOMITE° (if available)	20	120

CONFIDENTIAL AND PROPRIETARY

This document contains information that is confidential and proprietary to Smith & Nephew PLC and Smith & Nephew, Inc. and is intended for use only by Smith & Nephew and its manufacturer. It shall not be reproduced or copied in whole or in part, nor shall the contents be disclosed by any means without prior written permission from Smith & Nephew, nor shall anyone make any use of it that is contrary to the expressed or implied wishes of Smith & Nephew.

Study Protocol—Device	
Safety and Performance of PEEK Anchors (DYNOMITE°, SPYROMITE°, RAPTORMITE°, FOOTPRINT° ULTRA PK SL) in Extremities	Number: 2018.15.SMD.PEEK.RET.EXT
	Version: 2.0 05Dec2018
	Page: Page 6 of 54

	
 
 SPYROMITE° (if available)	20	120	
 
 FOOTPRINT ULTRA PK SL (If available)	20	120	
 
	SPYROMITE° (if available)	20	120	FOOTPRINT ULTRA PK SL (If available)	20	120
SPYROMITE° (if available)	20	120					
FOOTPRINT ULTRA PK SL (If available)	20	120					
Number of Study Sites:	Up to 15 sites						
Targeted Global Regions:	United States and/or Outside United States						
Inclusion Criteria:	
 Subjects who have undergone extremity joint repair using the study devices. Subjects aged 18 years and older at the time of surgery. 						
Exclusion Criteria:	
 Subject is entered in another investigational drug, biologic, or device study or has been treated with an investigational product within 12 months post-operative. Subjects who are < 3 months post-operative. 						
Study Duration:	Twelve month follow up.						
Primary endpoint:	Clinical success rate (%) of the study devices in extremities at 6 months post-operative. Clinical success is defined as extremity repairs without signs of device failure and/or re-intervention as assessed by the surgeon.						
Secondary endpoint(s):	Clinical success rate (%) of the study devices in extremities at 12 months post-operative. Clinical success has previously been defined.						
Other exploratory endpoint(s):	
Surgeon Reported Outcomes based on data collected in the subject's medical chart as standard of care at study sites. This may include but not limited to the following:
 
 Range of Motion (ROM) Pain assessed by Visual Analogue Scale (VAS) 						
Safety Data	
 All AEs, SAEs and complications including intra-operative adverse events and complications. 						

CONFIDENTIAL AND PROPRIETARY

This document contains information that is confidential and proprietary to Smith & Nephew PLC and Smith & Nephew, Inc. and is intended for use only by Smith & Nephew and its manufacturer. It shall not be reproduced or copied in whole or in part, nor shall the contents be disclosed by any means without prior written permission from Smith & Nephew, nor shall anyone make any use of it that is contrary to the expressed or implied wishes of Smith & Nephew.

Study Protocol—Device	
Safety and Performance of PEEK Anchors (DYNOMITE [®] , SPYROMITE [®] , RAPTORMITE [®] , FOOTPRINT [®] ULTRA PK SL) in Extremities	Number: 2018.15.SMD.PEEK.RET.EXT
	Version: 2.0 05Dec2018
	Page: Page 7 of 54

	
 • Device related intervention. • Device deficiency. • Concomitant medications/therapy.
--	--

CONFIDENTIAL AND PROPRIETARY

3.1 STUDY SCHEDULE

Table 1: Schedule of Events

Schedule of Events	Chart Review	
	6 months (182 days) post-op (+/- 90 days)	12 months (365 days) post-op (+/- 90 days)
Informed Consent	X N/A if waiver of consent approved by IRB	
Inclusion/Exclusion	X	
Demographics/Medical History	X	
Operative/Discharge Data Collection	X	
Implant Status	X	X
Pain assessed by VAS	X	X
ROM	X	X
Concomitant Medications or Therapies ¹	*	*
Serious Adverse Event (SAE)/Adverse Device Effect (ADE)/ Device Deficiency (DevD) Assessment	*	*
AE Assessment	*	*
End of Study/Subject Disposition	*	*

¹Any concomitant medications associated with an AE, SA(D)E will be recorded.

*As Needed

CONFIDENTIAL AND PROPRIETARY

This document contains information that is confidential and proprietary to Smith & Nephew PLC and Smith & Nephew, Inc. and is intended for use only by Smith & Nephew and its manufacturer. It shall not be reproduced or copied in whole or in part, nor shall the contents be disclosed by any means without prior written permission from Smith & Nephew, nor shall anyone make any use of it that is contrary to the expressed or implied wishes of Smith & Nephew.

Study Protocol—Device	
Safety and Performance of PEEK Anchors (DYNOMITE°, SPYROMITE°, RAPTORMITE°, FOOTPRINT° ULTRA PK SL) in Extremities	Number: 2018.15.SMD.PEEK.RET.EXT
	Version: 2.0 05Dec2018
	Page: Page 9 of 54

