7. OBJECTIVE(S)

7.1 PRIMARY OBJECTIVE

The primary objective of this study is to assess the safety and performance post-market of the PEEK Anchors (DYNOMITE[®], SPYROMITE[®], RAPTORMITE[®], FOOTPRINT[®] ULTRA PK SL) in extremities over a time period of 6 months after intervention.

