9.3 EXCLUSION CRITERIA

Any one (1) of the following criteria will disqualify a potential subject from participation in the study:

1. Subject is entered in another investigational drug, biologic, or device study or has been treated with an investigational product within 12 months post-operative.
2. Subjects who are < 3 months post-operative.

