9.7 LOST TO FOLLOW-UP

A subject will be considered lost to follow-up if he/she did not return for follow-up per the study Investigator’s standard of care follow-up schedule. Information will be documented on the Case Report Form (CRF).

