10.2 STUDY ENDPOINTS

10.2.1 Primary Endpoint

Clinical success rate (%) of the study devices in extremities at 6 months post-operative with clinical success defined as extremity repairs without signs of device failure and/or re-intervention as assessed by the surgeon.

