11. STUDY PROCEDURES

11.1 RETROSPECTIVE DATA COLLECTION: 6 MONTHS POST-OPERATIVE (±90 DAYS)

Given the retrospective study design, data will be collected from the medical chart to the extent it is available.

1. Subject should undergo the informed consent process and sign the informed consent *only* if a waiver of consent has not been approved by the IRB.
2. Screen the subject's chart for protocol inclusion/exclusion criteria.
3. Obtain demographic information and a medical history.
4. VAS, ROM.
5. Operative Data Collection – review operative case notes.

CONFIDENTIAL AND PROPRIETARY

This document contains information that is confidential and proprietary to Smith & Nephew PLC and Smith & Nephew, Inc. and is intended for use only by Smith & Nephew and its manufacturer. It shall not be reproduced or copied in whole or in part, nor shall the contents be disclosed by any means without prior written permission from Smith & Nephew, nor shall anyone make any use of it that is contrary to the expressed or implied wishes of Smith & Nephew.

Study Protocol—Device	
Safety and Performance of PEEK Anchors (DYNOMITE°, SPYROMITE°, RAPTORMITE°, FOOTPRINT° ULTRA PK SL) in Extremities	Number: 2018.15.SMD.PEEK.RET.EXT
	Version: 2.0 05Dec2018
	Page: Page 27 of 54

6. Implant Status/ Disposition.
7. Document concomitant medications and/or therapies associated with an AE, SA(D)E.
8. Review the subject’s chart for AEs, SAEs and Device Deficiencies, including inter-operative. AEs, SAEs and DevDs should be documented from the time of surgery through the study duration.

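### The 6-month success rate may be read anywhere from day 92 to day 272, so it depends partly on when routine visits took place

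*Combined protocol and SAP*

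**What the plan says.** The primary objective (section 7.1) is safety and performance "in extremities over a time period of 6 months after intervention". The primary endpoint (section 10.2.1) is "Clinical success rate (%) of the study devices in extremities at 6 months post-operative", with success defined as "extremity repairs without signs of device failure and/or re-intervention as assessed by the surgeon". The secondary endpoint applies the same definition at 12 months.

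Table 1 in section 3.1 records implant status at two chart reviews, "6 months (182 days) post-op (+/- 90 days") and "12 months (365 days) post-op (+/- 90 days"). Sections 11.1 and 11.2 repeat the windows. There are no study visits: "data will be collected from the medical chart to the extent it is available", and section 9.7 defines loss to follow-up against each investigator's "standard of care follow-up schedule". The only minimum on time since surgery is the exclusion in section 9.3: "Subjects who are < 3 months post-operative".

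Section 12.3 analyses the 6-month rate as a frequency and percentage with a two-sided 95% Clopper-Pearson interval, for all anchors combined and for each anchor. No section says which record counts when several fall in the window, whether status is cut at day 182, or how a subject last seen near day 92 is classified. Section 12 leaves the SAP to be written before database lock.

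**The concern.** Device failure and re-intervention accumulate, so a success rate has meaning only with a stated length of exposure. The window permits a latest reading day almost three times the earliest, and a single percentage has no way to reflect that.

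Two kinds of misclassification are open. A subject whose last record is on day 95, with nothing adverse noted, can enter as a 6-month success although days 96 to 182 were never observed. A subject whose anchor was intact on day 182, failed on day 250 and was seen on day 260 can enter as a 6-month failure.

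The first matters more here because the eligibility floor of 3 months sits at about the window's lower edge. A subject can be enrolled with almost no chart beyond that point.

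The per-anchor rates are more exposed than the pooled rate. Section 13 allows as few as 20 subjects per anchor and section 10.1 plans at least 10 per site, so two sites could supply an anchor's whole minimum sample and their visit habits would set its reading days.

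**Working it through.** **Inputs.** Windows: 182 ± 90 and 365 ± 90 days (Table 1). Assumed success: 91% per anchor; target interval 80% to 100%; 20 to 120 subjects per anchor; stated probability of that precision 15.2% to above 95% (section 13). Interval: two-sided 95% Clopper-Pearson (section 12.3). The documents give no distribution of failure times, so the shape below is an assumption.

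**The plan's own precision figure.** The target half-width is 91 − 80 = 11 points, so take a full width of at most 22 points as the criterion. At n = 20 only 20/20 meets it, with probability 0.91^20 = 0.152, the stated 15.2%. At n = 120 the probability exceeds 99.9%, consistent with above 95%. The 91% planning value is therefore a fair anchor for what follows.

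**Windows.** 182 − 90 = 92 and 182 + 90 = 272; 272/92 = 2.96. The 12-month window runs from 275 to 455.

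**Effect of the reading day.** Let S(t) = 0.91^((t/182)^k), a Weibull curve fixed at 91% on day 182. Shape k = 1 is a constant hazard, k < 1 means mostly early failures, and k > 1 means later failures.

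| k | Day 92 | Day 272 | Difference (points) | Mean if days spread evenly over 92–272 |
|---|---|---|---|---|
| 0.25 | 92.4% | 90.1% | 2.3 | 91.1% |
| 0.5 | 93.5% | 89.1% | 4.4 | 91.1% |
| 1 | 95.3% | 86.9% | 8.5 | 91.0% |
| 1.5 | 96.7% | 84.2% | 12.5 | 90.8% |
| 2 | 97.6% | 81.0% | 16.6 | 90.4% |

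The differences are taken before rounding. The day-92 and day-272 columns are extremes in which every subject is read on the same edge of the window.

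**Uneven timing, constant hazard.** With 75% of subjects read on day 92 and 25% on day 272: 0.75 × 95.34 + 0.25 × 86.85 = 93.2%. With the shares reversed: 0.25 × 95.34 + 0.75 × 86.85 = 89.0%. A fixed day-182 reading gives 91.0%.

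**Knock-on for precision.** At n = 20 under constant hazard, the chance of meeting the width target would be 0.9534^20 = 38.5% if all were read on day 92 and 0.8685^20 = 6.0% if all were read on day 272, against 15.2% as planned.

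**The case against.** The best defence is that the protocol is silent rather than wrong. Table 1 schedules a data item. It does not say that success is fixed by one visit day or that event dates are ignored. Adverse events and device deficiencies are abstracted from surgery onward (sections 11.1 and 11.2), events leading to revision are reported regardless of causality (section 14), and the SAP could still supply a fixed-day rule. A wide window is also a natural choice for a chart review without prospective visits. This stands in part: the misclassifications are permitted, not prescribed. But the current text gives a window, an eligibility floor and a crude percentage, and none of these stops the rate from drifting with visit timing.

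Four stronger readings are tempting, and the documents do not support them.

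- A reader might infer that the problem is just as large when every chart runs to 12 months. It is not. A re-intervention on day 150 is in a complete chart whatever the visit day. Dependence on visit timing is clearest for failures that were not operated on and for short charts.
- A reader might take 8.5 points as the expected bias. It is the gap between two extremes under one assumed hazard. The documents give no evidence on how visit days are actually distributed.
- A reader might treat the 3-day gap between the windows (272 and 275) as a flaw. Any adjacent, non-overlapping windows put subjects with similar follow-up on either side of a boundary.
- A reader might expect invalid comparisons between anchors, sites or time points. Section 12.3 plans estimates, pooled and per anchor, and no such tests. Section 13 says the study is not powered for hypothesis testing. What is affected is the interpretation of each estimate.

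**Conclusion.** The point holds in a limited form. As written, the plan lets the primary rate mix exposures from about 3 to about 9 months, and lets subjects with about 3 months of follow-up count as 6-month successes. Pooled and per-anchor rates therefore depend partly on visit timing.

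The size cannot be settled from the documents. Taking 91% at day 182, the extreme readings differ by 8.5 points under constant hazard and by 2.3 to 16.6 points over shapes 0.25 to 2, against a target half-width of 11 points. With evenly spread reading days the pooled mean stays within about 0.6 points of 91% for every shape tried (the largest departure is 91.0 − 90.4 at k = 2). Material bias needs reading days concentrated to one side of day 182. The plan neither prevents that nor would reveal it, because it does not report the day of assessment.

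It would be too strong to say that the reported figure cannot be a 6-month rate. It may be close to one, but the plan does not ensure it.

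**What to change.** In sections 10.2.1 and 10.2.2 and in the SAP, derive success from dates:

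1. Any re-intervention or device failure dated on or before day 182 (day 365 for 12 months) is a failure, whether or not a later record exists. This keeps early failures with no further chart entries.
2. A non-operated failure first noted at the in-window visit remains a 6-month failure unless the chart shows onset after day 182. Dating it simply to the day first noted would drop failures found at a slightly late 6-month visit and inflate success. The SAP should state the analysis date given to such a failure, so that the day-182 estimate includes it.
3. A subject without failure counts as a success only if event-free status is documented on or after day 182 (day 365). Otherwise the subject is censored at the last record.
4. Report Kaplan-Meier estimates with 95% confidence intervals at days 182 and 365, pooled and per anchor, beside the planned Clopper-Pearson windowed rate. The estimate assumes that stopping follow-up is unrelated to failure, and the report should say so.
5. Tabulate the day of assessment by anchor.

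Keep the ±90-day window for VAS and ROM.

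The cost is endpoint and SAP wording plus event and last-record dates from charts already under review. No visits or subjects are added. No case report form is among the documents, so its date fields need checking. Some onset dates will be approximate, and fewer subjects will contribute full 6-month information, so intervals may be slightly wider.

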4.2 LIST OF ABBREVIATIONS

Abbreviation	Definition
ADE	Adverse Device Effect(s)
AE	Adverse Event(s)
AOL	Activities of Daily Living
ASADE	Anticipated Serious Adverse Device Effect
CI	Confidence Interval
CRF	Case Report Form(s)
CSR	Clinical study Report
CTA	Clinical Trial Agreement
CV	Curriculum Vitae
DevD	Device Deficiency(ies)
EC	Ethics Committee
FU	Follow-Up
GCP	Good Clinical Practice
IBT	Iliotibial Band Syndrome
ICF	Informed Consent Form
ICH	International Conference on Harmonisation
IEC	International Ethics Committee
ICMJE	International Committee of Medical Journal Editors
IFU	Instructions for Use
IP	Investigational Product
IRB	Institutional Review Board
ISF	Investigator Site File

CONFIDENTIAL AND PROPRIETARY

This document contains information that is confidential and proprietary to Smith & Nephew PLC and Smith & Nephew, Inc. and is intended for use only by Smith & Nephew and its manufacturer. It shall not be reproduced or copied in whole or in part, nor shall the contents be disclosed by any means without prior written permission from Smith & Nephew, nor shall anyone make any use of it that is contrary to the expressed or implied wishes of Smith & Nephew.

Study Protocol—Device	
Safety and Performance of PEEK Anchors (DYNOMITE[®], SPYROMITE[®], RAPTORMITE[®], FOOTPRINT[®] ULTRA PK SL) in Extremities	Number: 2018.15.SMD.PEEK.RET.EXT
	Version: 2.0 05Dec2018
	Page: Page 13 of 54

Abbreviation	Definition
ISO	International Organization for Standardization
MEDDEV	Master Control European Medical Device Vigilance System
MDD	Medical Device Directive
NA or N/A	Not Applicable
NSAIDs	Nonsteroidal anti-inflammatory drugs
NSAE	Non-Serious Adverse Event(s)
PI	Principal Investigator
PP	Per-Protocol Population
ROM	Range of Motion
S&N	Smith & Nephew, Inc.
SADE	Serious Adverse Device Effect(s)
SAE	Serious Adverse Event(s)
SAF	Safety population
SAP	Statistical Analysis Plan
SOP	Standard Operating Procedures
SLAP	Superior Labral Tear from Anterior to Posterior
UHMWPE	Ultra-high molecular weight polyethylene
USADE	Unanticipated Serious Adverse Device Effect(s)
VAS	Visual Analog Scale

CONFIDENTIAL AND PROPRIETARY

5. INTRODUCTION

5.1 BACKGROUND

Suture Anchors are small fixation devices used in surgical procedures for attaching or reattaching tendons and ligaments to bone. The size and type of anchor used depends on the patient’s bone density and the procedure performed.

Suture anchors are made up of three components: the anchor - which is inserted into the bone; the eyelet – which is a hole or a loop in the anchor which the suture passes through to link the anchor to the suture; and the suture – which is attached to the anchor through the eyelet of the anchor. An anchor-receiving hole is first drilled in the bone at the desired point of tissue reattachment. A suture anchor is deployed in the hole using an appropriate installation tool. This effectively locks the suture to the bone, with the free end(s) of the suture extending out of the bone. Soft tissue is then moved into position over the hole containing the deployed suture anchor. As this is done, the free end(s) of the suture is (are) passed through or around the soft tissue so that the free end(s) of the suture reside(s) on the far (i.e., non-bone) side of the soft tissue. The suture is now used to tie the soft tissue securely to the bone.

Smith & Nephew (S&N) offers a variety of suture anchors including several polyetheretherketone (PEEK) suture anchors soft tissue to bone repair. The PEEK devices included in this review are all single use, sterile devices comprised of machined component anchor bodies that are manufactured from PEEK-OPTIMA Polymer (LT1). This material meets ISO 10993 biocompatibility requirements for implant devices, bone/tissue contact, and permanent contact. The anchor tips are molded components which are also manufactured from PEEK-OPTIMA Polymer (LT3). PEEK-OPTIMA polymers provide an ideal combination of strength, biocompatibility, revisability and inherent radiolucent characteristics. Smith & Nephew also provides a variety of reusable and

CONFIDENTIAL AND PROPRIETARY

This document contains information that is confidential and proprietary to Smith & Nephew PLC and Smith & Nephew, Inc. and is intended for use only by Smith & Nephew and its manufacturer. It shall not be reproduced or copied in whole or in part, nor shall the contents be disclosed by any means without prior written permission from Smith & Nephew, nor shall anyone make any use of it that is contrary to the expressed or implied wishes of Smith & Nephew.

Study Protocol—Device	
Safety and Performance of PEEK Anchors (DYNOMITE°, SPYROMITE°, RAPTORMITE°, FOOTPRINT° ULTRA PK SL) in Extremities	Number: 2018.15.SMD.PEEK.RET.EXT
	Version: 2.0 05Dec2018
	Page: Page 15 of 54

disposable instrumentation used in conjunction with the suture anchors including awls, dilators, drills, guides, obturators and wires.

5.2 STUDY PURPOSE

This is a retrospective study to evaluate intra-operative, 6 months and 12 months safety and performance of the PEEK anchors (DYNOMITE°, SPYROMITE°, RAPTORMITE°, FOOTPRINT° ULTRA PK SL) for extremities to meet existing MDD/MEDDEV requirements.

5.3 SAFETY CONSIDERATIONS

The PEEK suture anchor family, which include the following products: DYNOMITE°, SPYROMITE°, RAPTORMITE° and FOOTPRINT° ULTRA PK SL, are intended for reattachment of soft tissue to bone fixation in the joint extremities such as elbow, wrist, hand, foot and ankle. Representative language of the contraindications and potential adverse events can be found in the Instructions for Use (IFU) for each product.

Table 2: Instructions for Use Reference Numbers

PEEK Suture Anchor	IFU
DYNOMITE°	01/2017 10600401 Rev. D
SPYROMITE°, RAPTORMITE°	01/2017 10600400 Rev. D
FOOTPRINT° ULTRA PK SL	03/2017 10600402 Rev. E
	2017 10601001 REV. B

6. STUDY RELATED RISKS

6.1 STUDY POSSIBLE RISKS

As a result of participating in the study, there could be a risk of loss of protected subject information confidentiality. All applicable confidentiality standards and data protection and privacy laws will be

CONFIDENTIAL AND PROPRIETARY

This document contains information that is confidential and proprietary to Smith & Nephew PLC and Smith & Nephew, Inc. and is intended for use only by Smith & Nephew and its manufacturer. It shall not be reproduced or copied in whole or in part, nor shall the contents be disclosed by any means without prior written permission from Smith & Nephew, nor shall anyone make any use of it that is contrary to the expressed or implied wishes of Smith & Nephew.

Study Protocol—Device	
Safety and Performance of PEEK Anchors (DYNOMITE [®] , SPYROMITE [®] , RAPTORMITE [®] , FOOTPRINT [®] ULTRA PK SL) in Extremities	Number: 2018.15.SMD.PEEK.RET.EXT
	Version: 2.0 05Dec2018
	Page: Page 16 of 54

followed by the Sponsor to ensure that data collected is handled in confidence. Data will be coded and handled only by appropriately qualified and authorized personnel.

